Given the sample size of 15, we further estimate the statistical power of detecting differences in energy expenditure. Based on our recent pilot study on assessing resting metabolic rate (RMR) across 12 healthy, normal weight subjects (including both sexes, BMI:  $24.1 \pm 2.9$ , age: 25~71), we estimated that the within-subject variation in RMR is less than 0.15 kcal/min, whereas our instrument variation is less than 0.05 kcal/min within a day. Therefore, using the same cross-sectional design of 15 patients per arm, assuming we can detect a difference in RMR of 0.14 kcal/min (which is more than two times of the instrument precision), we can achieve a sufficient power of 80% with a significance level of 0.05 using a one-sided two-sample t-test.

For the exploratory aims, we plan to assess if the response to ThyPRO-39, a QoL questionnaire/instrument would yield significant difference between subjects on LT4/LT3 vs LT4 alone. We are also interested in

assessing potential genetic heterogeneity underlying the treatment group effect. More specifically, we would model the QoL endpoints using the ANOVA models incorporating treatment effect (LT4/LT3 vs LT4 alone), Thr92Ala D2 polymorphism (Thr/Thr, Thr/Ala, vs Ala/Ala), and their interaction effects. This would depict a better picture of which genetic group might benefit the most from LT4/LT3 combo therapy. This ANOVA modeling strategy can be extended in a straightforward manner to ANCOVA to assessing changes in other outcomes of interest, adjusting for potential genetic heterogeneity, as well as serum T3 level, and other important covariates.

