**D2 Polymorphism.** Epidemiologic, *in vivo*, and *in vitro* data support the hypothesis that the Thr92Ala D2 polymorphism (81) causes a reduction in the hormonal signaling due to a decrease in conversion of T4 into T3 (82-86). The Thr92Ala D2 polymorphism is associated with worse quality of life at baseline in hypothyroid patients, who responded better to LT3/LT4 combination therapy (39), but the results are not conclusive (87), and no prospective study has been performed to assess its role in the response to combination therapy. The prevalence of the minor Ala92 allele (81) will enable a Mendelian randomization, and we expect that 50% of the study population will be a carrier as heterozygous or homozygous. We do not expect to be able to detect a significant difference in any of the study outcomes as a consequence of the Thr92Ala D2 status, but the data gathered in this proof-of-concept study will enable to measure the point estimate for the modulatory role of the Thr92Ala D2, and if deemed relevant and feasible to design an adequately powered study. Genomic DNA extraction and genotyping will be performed in the Department of Endocrine lab. Briefly, genomic DNA isolated from whole

blood is amplified and genotyped using a SYTO 9 based PCR master mix containing primers specific to the DIO2

rs225014 (Thr92Ala) variant. PCR amplification and genotyping by small amplicon high-resolution melting (88) will be performed on the Applied Biosystems QuantStudio 3 real-time PCR system.

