## **9.6 Blood Collection**

### **Venous Blood Sample Collection**

We will insert a needle in a vein to collect blood samples at specified times. Study subjects will undergo one venipuncture during each of the study visits. Altogether, five blood samples will be collected throughout the study for a total of approximately one and a half cup of blood. All the samples collected will be for the research study, except for the measurement of TSH that will be used to adjust the therapy. We will store and analyze your samples for lipids (cholesterol, HDL, triglycerides), Thyroid stimulating Hormone TSH (determinations for dose adjustments), Free T4 and total T3. TPO antibodies and HbA1c or fructosamine < 325 mcmol/l in substitution of HbA1c to reflect recent improvement in diabetes control (the latter for patients with diabetes) will be collected at the screening visit to help determine the presence of autoimmune thyroid disease and, limited to patients with diabetes, the control of the disease. Blood samples will be collected at screening, baseline (pre-surgery), 3-month and 6-month study visits.

We will collect two 5 mL of blood will be collected in a Na-EDTA tube (purple top) at the baseline visit to obtain HbA1c and to extract genomic DNA. Approximately 20 mL of blood will be collected in SST tubes with (no additives except serum separator) each session for TSH, thyroid hormones (total T3 and free T4), serum lipids and storage. No more than 320 mL of blood will be collected over the course of the five sessions. Serum will be separated by centrifugation, aliquoted in 1 mL cryovials and stored in -80°C freezers in the Department of Endocrine laboratory in Sanger Hall. Samples will be stored as described above for future analyses for studies. The Thr92Ala D2 polymorphism will be analyzed in the Department of Endocrine laboratory. [name] will supervise the performance of these analyses.

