## **9.8 Genetic Material**

Genetic material will be collected during the study to study whether common gene variations called "Single Nucleotide Polymorphisms" (SNPs) in gene that regulate the thyroid hormone

signaling affect the response to the therapy. We do not plan to screen for genetic disease, and the information collected are without clinical interest, thus the information will not be provided to the volunteers. No genome wide association study will be performed, and the genetic material will be disposed of at the end of the study. Study volunteers can opt out the collection of genetic material.

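### Exploratory models only: with three genotypes crossed with arm in 30 patients, the Ala/Ala interaction will often be inestimable or rest on one patient; a one-degree-of-freedom coding should be fixed in advance

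*Combined protocol and SAP*

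**What the plan says.** The Protocol Summary, under Statistical Methodology, models the quality-of-life endpoints by ANOVA with treatment, "Thr92Ala D2 polymorphism (Thr/Thr, Thr/Ala, vs Ala/Ala), and their interaction effects". The stated aim is: "This would depict a better picture of which genetic group might benefit the most from LT4/LT3 combo therapy". The same paragraph says the approach can be extended to ANCOVA for changes in other outcomes, "adjusting for potential genetic heterogeneity, as well as serum T3 level, and other important covariates". The Endpoints list gives the effect of the D2 variant on the primary and secondary endpoints as exploratory.

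Section 3.4 supplies the only frequency: "we expect that 50% of the study population will be a carrier as heterozygous or homozygous". It gives no separate Ala/Ala share. It is frank about power ("We do not expect to be able to detect a significant difference in any of the study outcomes") but keeps a deliverable: "the data gathered in this proof-of-concept study will enable to measure the point estimate for the modulatory role of the Thr92Ala D2". Section 9.8 adds: "Study volunteers can opt out the collection of genetic material". No section says what happens if a genotype-by-arm cell is empty.

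T3 is drawn before surgery and at months 3 and 6, but the ANCOVA sentence does not say which draw is the covariate. Section 9.6 describes the analytes as "thyroid hormones (total T3 and free T4), serum lipids and storage", while Table 1 (Schedule of Events) and Sections 10.3.2, 10.5 and 10.6 list Free T3. ThyPRO-39 is taken at baseline (Section 9.9), but its baseline value is not named as a covariate.

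**The concern.** Six cells filled from 30 patients leave little for the rarest genotype. If an arm has no Ala/Ala patient, the Ala/Ala part of the interaction does not exist, and neither does an arm effect averaged over all three genotypes in that model. If an arm has one such patient, that person's outcome is the cell mean. Sections 1 and 4 present the study as a source of point estimates for a larger trial, and Section 3.4 wants one for this variant. A coding that often yields no usable estimate for one of three named groups works against that aim.

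Two smaller matters sit in the same paragraph. The ANCOVA lists a covariate that could be read as on-treatment T3, and it leaves out the covariate most likely to help, the baseline value of the outcome.

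**Working it through.** The plan gives no cell count or power for the genotype model, so there is no stated figure to reproduce. As a check on 15 per arm, a one-sided noncentral-t calculation at 0.05 gives 62.7% for 1.4 kg with SD 1.9 kg, as in the plan's weight table.

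**Inputs.** 30 patients, 1:1, so 15 per arm (Section 4). Carriers 50% (Section 3.4). Assumptions: Hardy-Weinberg proportions and everyone genotyped.

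**Genotype shares.** (1 − q)² = 0.50, so q = 1 − √0.50 = 0.293 and Ala/Ala = q² = 0.0858. Expected per arm: Ala/Ala 15 × 0.0858 = 1.29; Thr/Ala 15 × 2 × 0.293 × 0.707 = 6.2; Thr/Thr 7.5.

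**Empty cell.** P(no Ala/Ala in one arm) = 0.9142^15 = 0.260. P(at least one arm with none) = 1 − (1 − 0.260)² = 0.453.

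| Carriers | Genotyped per arm | At least one arm with no Ala/Ala |
|---|---|---|
| 40% | 15 | 71% |
| 50% | 15 | 45% |
| 60% | 15 | 21% |
| 50% | 14 | 49% |
| 50% | 13 | 53% |
| 50% | 12 | 57% |

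The last three rows assume an opt-out level, since the documents give none.

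**None or one.** P(none or one in an arm) = 0.627, so P(at least one arm with none or one) = 1 − (1 − 0.627)² = 0.861. Both arms have two or more in only 13.9% of cases.

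**Precision.** The documents give no SD for ThyPRO-39, so widths are in residual SD units. For cell contrasts the 95% half-width is t(0.975) × √(sum of 1/cell size); the allele count uses the within-arm spread of the count instead. Medians over 40,000 simulated allocations:

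| Interaction contrast | Median half-width | For weight, × 1.9 kg |
|---|---|---|
| Ala/Ala vs Thr/Thr (estimable in 55% of draws) | 2.73 SD | 5.2 kg |
| Thr/Ala vs Thr/Thr | 1.63 SD | 3.1 kg |
| Carrier vs non-carrier | 1.55 SD | 2.9 kg |
| Per allele (linear trend assumed) | 1.25 SD | 2.4 kg |

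The carrier contrast at expected counts has SE √(4/7.5) = 0.73 SD. With 26 degrees of freedom, two-sided power for a 1 SD interaction is about 26%.

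**Baseline outcome.** With equal variances and baseline to month-6 correlation r, the SE of a baseline-adjusted comparison relative to a change-score comparison is √((1 + r)/2). For r = 0.5 this is √0.75 = 0.87; for r = 0.7 it is √0.85 = 0.92. These correlations are assumed.

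**T3.** Statistical Methodology expects T3 about 44% higher on LT3/LT4 than on LT4. Sections 1 and 2.1 propose that rise as the mechanism. A month-3 or month-6 value is therefore an effect of treatment, and adjusting for it would remove whatever part of the benefit runs through T3. A pre-surgery value carries no such risk.

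**The case against.** The strongest reply is that Section 3.4 already concedes the point: it expects no significant genotype finding, treats the analysis as exploratory, never promises an Ala/Ala-specific estimate, and groups carriers as heterozygous or homozygous. That answers a complaint about power. It does not answer one about estimability, because the model actually written down has three levels and is meant to show which genetic group benefits most.

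A second reply is that recoding gains little: the heterozygote contrast has half-width 1.63 SD and carrier coding 1.55 SD. That stands as to precision. The gain is one pre-defined estimate that practically always exists. A pooling rule triggered by an empty cell would be simpler, but it would leave the more frequent case of a single patient in a cell.

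Third, the plan works with changes from baseline (Statistical Methodology, Section 3.4), so baseline is not ignored. That is right, and the gain from adding it as a covariate is therefore measured against change scores.

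A reader might infer that T3 adjustment will erase the treatment effect. The documents do not support that: they say only that the model can be extended, name no draw, and leave the baseline value available. Nor does the missing visit mean T3 is not drawn; it is scheduled three times.

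**Conclusion.** The point holds for the exploratory models. The 45% figure rests on 50% carriers, Hardy-Weinberg proportions and complete genotyping; 21% to 71% is a fair range for the carrier share, and opt-outs push it up. The 86% figure for none or one Ala/Ala patient in an arm rests on the same assumptions.

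It would be too strong to conclude that the trial's main comparisons are compromised. The t-tests powered for weight, LDL and resting metabolic rate contain neither genotype nor T3. It would also be too strong to say that every treatment estimate is safe: in the three-level interaction model, an arm effect averaged over genotypes is lost when a cell is empty. The T3 timing and assay matters are secondary clarifications. Overall the weight is minor to moderate, and the plan should be changed.

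**What to change.** - Fix in advance a one-degree-of-freedom genotype-by-arm interaction: carrier versus non-carrier (the grouping in Section 3.4) or allele count 0/1/2. Report it with a 95% confidence interval and the number genotyped in each arm. Describe Ala/Ala patients by arm without a model.
- Include the baseline value of the outcome as a covariate in models that estimate the treatment effect.
- If T3 is a covariate in such a model, allow only the pre-surgery draw. Label any model with month-3 or month-6 T3 as mediation or dose-response.
- Reconcile total T3 in Section 9.6 with Free T3 in Table 1 and Sections 10.3.2, 10.5 and 10.6.

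The cost is wording: no patients, visits or samples are added. Carrier coding imposes a dominant form and allele count an additive one, so neither separates heterozygous from homozygous effects. Precision stays low, and the interval should be presented as such. Each baseline covariate uses one degree of freedom.

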**Study Design:**

**This is a pilot, randomized, double-blind, controlled, parallel study** in which thirty patients will be phenotypically characterized at baseline before surgery, 3 and 6 months following surgery. There will be one 6 week post-surgery dose adjustment visit. Both groups will receive active therapy for the treatment of hypothyroidism: either LT4 and placebo or LT4/LT3 combination therapy.

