**Statistical Methodology:**

Our preliminary estimate is based on the findings of our cross-over study with a population of 14 patients (13 female, weight (kg) =  $69.7 \pm 12.5$ , age (years) =  $49.3 \pm 8.0$ ). After substitution of LT3 for LT4 a decrease in weight was  $1.8 \pm 1.9$  kg, and in LDL-cholesterol was 13%. In this study LT3 treatment resulted in 85% higher morning serum T3 level as compared to LT4. From our recent study, the estimated increase in serum T3 level on LT3/LT4 combination therapy adopted in the current proposal would be about 44% as compared to LT4 alone, approximately half of the increase in serum T3 observed with full LT3 substitution. Using the point estimates of our recent meta-analysis, the predicted weight gain occurring after thyroidectomy is 1.4 to 2.2 Kg. Similarly, no study has measured changes in energy expenditure using WRIC in similar study populations, and our crossover intervention did not show significant differences in REE between LT3 only and LT4 treatments despite a significant change in body weight.

We hypothesize that LT3/LT4 therapy will be superior to LT4, likely to a smaller effect than LT3 alone. We do not expect that the effect would be larger than that of pure LT3 therapy. On the other hand, the complex interaction of LT4 and LT3 means that an optimal combination ratio may exist theoretically that outperforms the pure LT3 therapy. Based on our empirical observations and extrapolations, we enumerate a few possible effect size to estimate the required sample sizes in a two-arm, randomized, cross-sectional design, given a significance level of 0.05. The following sample size calculation and statistical power estimation are obtained based on two-sample, one-sided t-test based on weight loss in LT3/LT4 as compared to LT4 alone.

Weight Loss LT3/LT4	SD (kg)	Power (%)	Sample Size per	Weight Loss LT3/LT4	SD (kg)	Power (%)	Sample Size per
1.4	1.9	62.7	15	1.4	1.9	80.8	24
1.6	1.9	72.7	15	1.6	1.9	81.6	19
1.8	1.9	81.2	15	1.8	1.9	81.2	15
2.0	1.9	87.8	15	2.0	1.9	80.3	12
2.2	1.9	92.6	15	2.2	1.9	80.1	10
1.4	2.3	49.3	15	1.4	2.3	80.9	35
1.6	2.3	58.5	15	1.6	2.3	81.0	27
1.8	2.3	67.2	15	1.8	2.3	80.2	21
2.0	2.3	75.1	15	2.0	2.3	81.9	18
2.2	2.3	81.9	15	2.2	2.3	81.9	15

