Notice that even if the primary endpoints are expressed as differences between baseline and end of the study, in the LT3/LT4 vs LT4 alone groups, we are collecting phenotypic data at each follow-up time point. This will offer great opportunities to characterize the longitudinal profiles of these phenotypic data and to estimate the effect size as well as the standard deviation over time, essentially the trajectory of these measured endpoints over the 6-month time period. Ultimately, this would help size a much more powerful study that analyzes the repeated measures of the phenotypic data, or design a sufficiently powered study with a limited number of subjects due to the elimination of inter-subject variation. For example, with 4 time points planned for the study, even if the power to assess the treatment effect difference on the weight loss of 1.4 (SD=1.9) is 62.7% given a sample size of 15 vs 15 (LT4/LT3 vs LT4 alone), the power to detect the treatment by time effect could range from 80% up to 95% depending on mean trajectory change, and the correlation structures between measurements at different time points from a repeated measures ANOVA/ANCOVA modeling. We believe this is a significant strength in our dense phenotyping approach with multiple time points, particularly in consideration of the exploratory scope of the R21 funding mechanism.

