# SCHEMA

**Table 1: Schedule of Events.**

Procedures	Screening	Baseline	6 Weeks**	3 Months**	6 Months**
Informed Consent	X				
Confirm Inclusion/Exclusion	X				
Medical History	X	X	X	X	X
Physical Examination	X	X	X	X	X
Weight	X				
Vital Signs	X				
TSH a	X	X	X	X	X
HbA1c a or Fructosamine	X				
TPO Antibodies a	X				
24 Hour Resting Energy Expenditure (Whole Room Indirect Calorimeter) b		X		X	X
Genomic DNA*		X			
Free T4*		X		X	X
Free T3*		X		X	X
Lipids* a		X		X	X
Serum Storage*		X	X	X	X
Echocardiogram		X		X	X
ThyPro-39 Quality of Life Questionnaire		X		X	X
DXA scan		X			X
Randomization		X			
Study drug dispensation		X	X	X	
Dosing Adjustments			X	X	

- \* Analyses run in the Department of Endocrine Lab
- \*\* +/- 7 days
- a Analyses run in the VCU Health Department of Pathology
- b Visit in Whole Room Indirect Calorimeter may be up to 24 hours

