analysis algorithm to overcome the suboptimal temporal resolution issue associated with traditional WRICs. This method minimizes the latency between events and response in EE recordings and enable truly minute-by-minute real-time monitoring capability of WRIC (61). Additionally, the continuous recording of the respiratory quotient (RQ) during controlled fasting enables us to assess substrate utilization and metabolic flexibility, which correlates well with the risk of developing metabolic complications from obesity (62). The real-time monitoring capability of WRIC, coupled with precise event annotation and timestamping as well as the wearable sensors that collect other physiological data simultaneously, allows for analysis of each component of EE. For example, the thermic effect of food can be found by aggregating the post-prandial EE 4-hours after the meal time. Sleeping/wake onset times can be detected using wearable activity sensors (63) and sleeping EE can be found by aggregating EE between sleep time and wake onset time. While no exercise will be conducted in our study, we also plan to monitor minute-by-minute activity counts and assess the impact of spontaneous activities on EE in our analysis. The optimized temporal response of our WRIC system, and expertise in wearable data collection and analysis, will in turn make the VCU whole room indirect calorimeter system uniquely poised to record small differences in the EE and its components. For the purpose of this study, we will perform 24-hour recordings of EE in the VCU WRIC which has a precision of 0.05 Kcal/min. In preliminary experiments performed in a group of liver transplant patients with or without non-alcoholic fatty liver disease (NAFLD), we were able to detect a significant difference in RQ during controlled fast (Figure 4) indicating that NAFLD adversely affects metabolic flexibility in this population. These data show that the VCU WRIC system is uniquely positioned to detect small differences in EE components which over time can result in significant weight changes. In our study design, study participants will undergo a total of three 24-hour EE recordings before, three, and six months after total thyroidectomy while on LT4 alone or LT3/LT4 therapy. Weight will be measured by a stadiometer at the end of each EE recording, following 15-hour fasting, after voiding. Body composition will be measured by DXA scan at baseline and at the completion of the study.

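### The 80–95% treatment-by-time power quoted for weight is not supported by the weights the protocol schedules, and the weight schedule itself is inconsistent

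*Combined protocol and SAP*

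**What the plan says.** The last paragraph of the Protocol Summary's Statistical Methodology sets two figures side by side. The first is the two-arm comparison at 15 per arm, where the power for "the treatment effect difference on the weight loss of 1.4 (SD=1.9) is 62.7" per cent. The second is for repeated measures: "with 4 time points planned for the study", "the power to detect the treatment by time effect could range from 80% up to 95% depending on mean trajectory change". The model is named only as repeated measures ANOVA/ANCOVA. Trajectory and correlation are named as drivers without values. The paragraph presents the multiple time points as a significant strength.

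The SD comes from the sponsor's crossover study, described earlier in the same section: "After substitution of LT3 for LT4 a decrease in weight was" 1.8 ± 1.9 kg. Body weight in those patients had an SD of 12.5 kg. So 1.9 kg is the SD of a within-patient change.

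On timing, the Study Design paragraph says that "thirty patients will be phenotypically characterized at baseline before surgery, 3 and 6 months following surgery". Section 3.1 is explicit: "Weight will be measured by a stadiometer at the end of each EE recording, following 15-hour fasting, after voiding", and there are three such recordings. "Table 1: Schedule of Events" marks weight at screening only. Section 10.2 lists weight at screening. Sections 10.3, 10.4, 10.5 and 10.6 do not list it, the abbreviated examination in section 9.3 does not contain it, and section 9.5 gives the method without visits.

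**The concern.** A reader of the summary learns that analysing the trajectory could turn a 63% study into an 80–95% study for a primary endpoint. If the scheduled weights do not deliver that, a non-significant treatment-by-time result could be over-read as evidence of no difference.

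The fourth weight is also unaccounted for. The 6-week visit is the obvious candidate, but no weight is stated there. Staff who work from Table 1 or the visit lists are not told to weigh patients at baseline, 3 or 6 months, although weight change over that period is a primary endpoint.

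**Working it through.** **Inputs from the plan.** Difference 1.4 kg; SD of change 1.9 kg; n = 15 per arm; α = 0.05; one-sided two-sample t-test for the base figure.

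**Plan's base figure.** Noncentrality 1.4 / (1.9 × √(2/15)) = 2.018 on 28 df. One-sided power is 62.7%, so the plan's figure reproduces.

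**Method for treatment by time.** For between-arm differences d at the visits, covariance Σ and successive-difference contrasts C, λ = (n/2)(Cd)′(CΣC′)⁻¹(Cd). The multivariate F for m visits has m−1 and 28−(m−1)+1 df. The best single contrast is a t-test on 28 df with noncentrality √λ. Σ is scaled so that the SD of the 0–6 month change is 1.9.

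**Assumptions of mine, not in the plan.** Trajectories rise to 1.4 kg without overshoot. Correlation is either compound symmetry (CS) or AR-type, with correlation 0.5–0.99 over 6 months. Screening is 0.5–2 months before baseline.

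**Worked case: three weights, CS, linear.** d = 0, 0.7, 1.4, so Σ(d−d̄)² = 0.98. The residual variance is 1.9²/2 = 1.805. Then λ = 7.5 × 0.98/1.805 = 4.07, which is 2.018². The middle visit adds no information to the best contrast, and the F-test spends an extra degree of freedom. With the full effect by 3 months, Σ(d−d̄)² = 1.307 and λ = 5.43.

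| Weights | Path to 1.4 kg | λ (CS) | Multivariate F: CS / AR-type (%) | Best one-sided contrast: CS / AR-type (%) |
|---|---|---|---|---|
| 0, 3, 6 mo | linear | 4.07 | 38.2 / 38.2 | 62.7 / 62.7 |
| 0, 3, 6 mo | full by 3 mo | 5.43 | 49.1 / 61.0–67.2 | 73.5 / 83.0–87.2 |
| Screening + these | linear | 5.60 | 42.7 / 31.8–32.6 | 74.7 / 62.7–63.7 |
| Screening + these | full by 3 mo | 8.14 | 59.0 / 52.9–58.9 | 87.3 / 83.2–87.2 |
| 0, 6 wk, 3, 6 mo | linear | 4.45 | 34.5 / 31.8 | 66.1 / 62.7 |
| 0, 6 wk, 3, 6 mo | full by 6 wk | 6.11 | 46.2 / 81.1–89.5 | 77.8 / 96.9–98.9 |
| 0, 6 wk, 3, 6 mo | step at month 3 | 8.14 | 59.0 / 81.2–89.5 | 87.3 / 97.0–98.9 |

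**Univariate F, three weights.** Under CS it gives 40.3% (linear) and 51.6% (full by 3 months). Under AR-type correlation, simulation gives 50–53% and 64–67% uncorrected, or 47–49% and 60–62% with the Greenhouse–Geisser correction. Across both F-tests the range is therefore 38–53% (linear) and 49–67% (full by 3 months).

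**1.9 kg as a per-visit SD.** With correlation 0.8 (CS), the SD of change is 1.9 × √(2 × 0.2) = 1.20 kg. The three-weight F-tests then give 77.5–80.0% (linear) and 88.6–90.5% (full by 3 months). On that reading the simple change test has 92.9%, not the 62.7% beside it.

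**Baseline adjustment.** SDs of 12.5 and 1.9 kg imply a correlation of 1 − 1.9²/(2 × 12.5²) = 0.988. The ANCOVA residual SD is 12.5 × √(1 − 0.988²) ≈ 1.89 kg, so covariate adjustment adds almost nothing to a change-score analysis.

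**The case against.** The strongest reply is that the plan's statement assumes four points, not three, and says only that power *could* range that high depending on trajectory and correlation. That stands. With a 6-week weight and AR-type correlation, two abrupt trajectories reach 81–90% by multivariate F and 97–99% by the best one-sided contrast, with 1.9 kg kept as the SD of change. A reader might infer that the range is an arithmetic impossibility; the documents do not support that.

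A reader might also infer that the author mistook 1.9 kg for a per-visit SD, since the paragraph speaks of gains "due to the elimination of inter-subject variation". That is conjecture. The phrase is attached to the design of a later study, and the paragraph does not show how the range was obtained. All that can be said is that the per-visit reading would contradict the 62.7% in the same sentence.

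The consequences are also limited. The sentence is offered as an example; the sample size is dictated by time and funding; and the later trial is to be sized from the pilot's observed estimates.

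On the schedule, section 3.1 already gives the answer. Table 1 is not exhaustive: vital signs are marked at screening only, yet section 9.3 includes them in the examination done at every visit. Weight also enters the energy-needs equation at each phenotyping visit. So it would be wrong to conclude that weight is not planned after screening, or that a 6-week weight is ruled out. What remains is that none is stated at 6 weeks and that the operational lists omit weight throughout follow-up.

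**Conclusion.** The 80–95% figure cannot be reproduced from what the plan states and is not supported by the scheduled weights. At 0, 3 and 6 months, with 1.9 kg as the SD of change, no F-test examined exceeds about 67%, and a linear trajectory gives 38–53%. Reaching 80% needs an abrupt effect, AR-type correlation and a one-sided single contrast together. The maximum found is 87%, so 95% is not reached. Adding the screening weight does not change this: its multivariate F stays at 32–59% and its best contrast at 63–87%. Even with a 6-week weight, a linear trajectory leaves the multivariate F at 32–35%.

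These ranges rest on the trajectory and correlation assumptions listed above, which the plan neither confirms nor excludes. The figure is unsupported, not impossible, and the sample size does not depend on it. The inconsistency over when weight is measured is a separate matter and rests on reading alone.

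**What to change.** 1. Delete the 80–95% sentence. Alternatively, restate it for the weights actually scheduled, giving the SD of change (the same 1.9 kg that underlies the 62.7%), trajectory, correlation structure, test and sidedness, with the linear case shown.
2. For weight, replace the reference to four time points with the visits at which weight is measured.
3. Correct Table 1 and sections 10.3, 10.5 and 10.6 to list weight at baseline, 3 and 6 months, as section 3.1 already requires.

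A 6-week weight is not needed for any of this. The cost is text and table edits only, with no added patient, visit or measurement. The downside is a less favourable stated power.
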